#### 14.8 Secondary endpoint analysis

The primary analysis will be repeated using the secondary endpoints.

The primary and secondary endpoints will also be used to perform analyses comparing the difference in response between the abatacept and placebo groups with the biomarker positive group against the difference in response between the abatacept and placebo groups with the biomarker negative group.

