#### 1.1 Background

A previous observational study performed at the Centre of Experimental Medicine and Rheumatology called the 'Pathobiology of Early Arthritis Cohort' (PEAC) demonstrated the presence of three distinct pathology groups in patients with RA; namely the a) lympho-myeloid b) diffuse-myeloid and c) pauci-immune pathotypes. These pathotypes are characterised by the a) presence of B cells and myeloid cells b) cells of the myeloid lineage but poor in B cells and c) scarce immune cells with a predominance of stromal cells in the synovium respectively. In addition to histological analysis of the synovium, molecular analysis of the synovium was also undertaken by RNA sequencing. The lympho-myeloid phenotype was found to be associated with the highest level of erythrocyte sedimentation rate (ESR), C- reactive protein (CRP), anti-citrullinated protein antibody (ACPA) titre and DAS-28 ESR scores as well as greater erosive disease and a higher 'inflammatory signal on ultrasound. The pauci-immune pathotype on the other hand was associated with the lowest levels of ESR and CRP, rheumatoid factor (RF) and ACPA positivity and US scores despite high DAS-28 ESR scores. At a molecular level, gene expression signatures were found to correlate with response to csDMARD therapy. For example, the myeloid and lymphoid scores were associated with greater response to csDMARDs as measured by larger decreases in DAS28-ESR posttreatment.

Abatacept is indicated for moderate to severe active rheumatoid arthritis (RA) in adult patients who responded inadequately to previous therapy with one or more disease-modifying antirheumatic drugs (DMARDs) including methotrexate (MTX) or a tumour necrosis factor (TNF)alpha inhibitor. In this trial DMARD naïve RA patients with <12 months symptom duration will receive MTX + placebo or MTX + abatacept, so abatacept is prescribed "off-label" for patients at this stage of RA disease. Abatacept has been used in a number of early intervention trials and safety and efficacy as an early RA intervention has been demonstrated in the following trials: NORD-STAR^4, AGREE and AVERT. For example, in the NORD-STAR trial, compared with active conventional therapy, CDAI remission rates were significantly higher for abatacept. Additionally, in the trial, the proportion of SAEs was lowest in the abatacept group when compared to certolizumab, tocilizumab and active conventional therapy.

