#### 2.3.2 Secondary endpoint(s)

- 1. Percentage of patients with DAS28<3.2 (LDA) at 16 weeks.
- 2. Percentage of patients deemed responders using American College of Rheumatology 50 (ACR50) measure at 16 weeks.
- 3. Percentage of patients with CDAI remission at 16 weeks.
- 4. Change in HAQ-DI at 16 weeks from baseline.
- 5. Change in SF-36 at 16 weeks from baseline

Secondary endpoints will be reported descriptively within each treatment group.

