#### 2.5 Objectives and end points summary

Primary Analysis	Primary Endpoint	Outcome Measure
To determine whether synovial molecular profiles can inform treatment response to abatacept in early RA.	The primary endpoint of the study will be the delta CDAI at 16 weeks	Delta CDAI
Secondary Analyses	Secondary Endpoint	Outcome Measure
To use alternative outcome measures to assess the robustness of	Percentage of patients with DAS28 ≤2.6 (LDA) at 16 weeks.	DAS28(ESR) ≤2.6
the primary analysis	Percentage of patients deemed responders using American College of Rheumatology 50 (ACR50) measure at 16 weeks.	ACR50
	Percentage of patients with CDAI remission at 16 weeks.	CDAI remission (≤2.8)
	Change in HAQ-DI at 16 weeks from baseline.	HAQ-DI
	Change in SF-36 at 16 weeks from baseline	SF-36

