#### 14.4 Statistical Analysis

The statistical analysis of the trial will be described in detail in the Statistical Analysis Plan (SAP). This will be finalised prior to the analysis of the data. In brief, the primary outcome, which is a continuous outcome, will be analysed by analysis of covariance (ANCOVA) with treatment as a factor and baseline value as continuous covariate. If assumptions for ANCOVA are not met, non-parametric ANCOVA will be used. Changes from baseline within groups will be analysed with a paired Wilcoxon test. Secondary binary endpoints will be analysed using a  $\chi^2$  test unless any element within the contingency table has fewer than 5 individuals in which case a Fisher's exact test will be used.

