#### 14.7 Primary endpoint analysis

The primary analysis is within the abatacept arm. It will assess the difference in the change in Clinical Disease Activity Index (CDAI) score at 16 weeks between the biomarker positive and the biomarker negative patients (i.e. Group 1 vs Group 3). This analysis will be on an ITT basis according to original randomisation allocation. The primary outcome will be analysed by analysis of covariance (ANCOVA) with treatment as a factor and baseline value as continuous covariate. If assumptions for ANCOVA are not met, non-parametric ANCOVA will be used. The treatment effect will be reported as least squares mean with 95% confidence intervals.

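### The binary robustness repeats of the Group 1 v Group 3 comparison drop the baseline adjustment, so the two absolute-threshold endpoints mix baseline disease activity with response

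*Protocol*

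**What the plan says.** Section 14.7 fixes the primary comparison: "The primary analysis is within the abatacept arm", Group 1 against Group 3, by "analysis of covariance (ANCOVA) with treatment as a factor and baseline value as continuous covariate". Only one treatment is present in that comparison, so the factor has to be read as biomarker status.

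Section 14.8 carries the comparison over: "The primary analysis will be repeated using the secondary endpoints". The table in section 2.5 gives the purpose: "To use alternative outcome measures to assess the robustness of" the primary analysis.

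Three of the five secondary endpoints in section 2.3.2 are binary:
- "Percentage of patients with DAS28<3.2 (LDA) at 16 weeks" (section 2.5 gives a different cut-off, ≤2.6, for what appears to be the same endpoint);
- "Percentage of patients deemed responders using American College of Rheumatology 50 (ACR50) measure at 16 weeks";
- CDAI remission at week 16, defined in section 2.5 as ≤2.8.

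For these, section 14.4 says: "Secondary binary endpoints will be analysed using a" χ² test, with Fisher's exact test when a cell is small. Section 2.3.2, by contrast, says that secondary endpoints are only described within each treatment group.

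Section 7.3 randomises drug against placebo within biomarker status. Groups 1 and 3 therefore differ by a patient trait, not by allocation.

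**The concern.** In a randomised comparison an unadjusted χ² test is valid and merely less efficient. Here the groups are defined by a baseline trait, so their starting disease activity need not be equal. The primary ANCOVA asks whether the groups differ given baseline. The χ² test asks whether the crude proportions differ. These are different hypotheses whenever baselines differ and the endpoint is a fixed week-16 level, because a patient who starts higher reaches the level less often for the same response.

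At stake is the stated purpose of these endpoints. A check meant to confirm the primary result could appear to contradict it, or could reject when the biomarker has no effect, only because the groups started at different points.

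**Working it through.** **The plan's own figure.** Section 14.1 uses a difference of 10 and SD 14.34. The protocol text does not state alpha; 5% two-sided is assumed. Per group, n = 2(1.960 + 1.282)² × 14.34²/10² = 43.2, so 44 at 90% power; with 0.842 in place of 1.282 it is 32.3, so 33 at 80%. Four groups need 176 (132). Dividing by 0.90 gives 196 (147). All stated figures reproduce, and 44 per group is used below.

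**Assumed values, not in the protocol.** Baseline CDAI has mean 30 and SD 12. Week-16 CDAI = 12 + slope × (baseline − 30) + noise with SD 11, and slope is 0.4 to 0.6. There is no biomarker effect given baseline. The baseline gap between biomarker groups is 0 to 8 points.

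**Hand check at a 6-point gap, CDAI ≤2.8.** The gap passes slope × 6 into the week-16 means.
- Slope 0.4: means 13.2 and 10.8; SD = √(0.4² × 12² + 11²) = 12.0. Proportions are Φ(−10.4/12.0) = 19% and Φ(−8.0/12.0) = 25%.
- Slope 0.6: means 13.8 and 10.2; SD = √(0.6² × 12² + 11²) = 13.1. Proportions are Φ(−11.0/13.1) = 20% and Φ(−7.4/13.1) = 29%.

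With 44 per group the standard error of the difference is about 0.09. These differences are therefore about 0.7 and 0.9 standard errors, which gives rejection rates of about 10% and 16%.

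**Simulation, same model, CDAI ≤2.8, χ² (Fisher if a cell is below 5).**

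| Baseline gap | Unadjusted rejection |
|---|---|
| 0 | about 4-5% |
| 3 | 6-8% |
| 6 | 10-15% |
| 8 | 13-23% |

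Logistic regression with baseline CDAI rejects about 5-6%.

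**Other assumptions.** With week-16 mean 14, residual SD 12 and slope 0.3 to 0.5, unadjusted rejection for CDAI ≤2.8 was 3.1-4.0% at no gap, 4.7-9.4% at 6 points and 7.0-17.0% at 9 points. The direction is the same and the size smaller.

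**ACR50.** With a fall of at least 50% in CDAI as a rough stand-in, unadjusted rejection stayed at about 4-8% across all gaps and both sets of assumptions.

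**Power with equal baselines.** For a 10-point effect on CDAI ≤2.8, power is about 81-82% adjusted and 72-79% unadjusted.

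The DAS28 cut-off was not simulated. It is exposed to the same mechanism, but its size is not quantified here.

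**The case against.** The strongest objection is that no baseline gap has been shown. A reader might infer from section 1.1 that the crude test is shifted against biomarker-positive patients: "The lympho-myeloid phenotype was found to be associated with the highest level of erythrocyte sedimentation rate", and also with the highest CRP and DAS28-ESR. The protocol does not support that as a fact. Section 1.1 describes pathotype, whereas the trial biomarker is CD80/CD86 status (sections 2.6 and 7.3), and section 2.1 connects the two only as a hypothesis. Section 1.1 also reports high DAS28-ESR scores in the pauci-immune group. DAS28-ESR contains ESR and CDAI does not (section 7.6.4), so a difference driven by ESR need not appear in CDAI. This stands: a gap is plausible, but its size and sign are unknown.

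A reader might also infer that adjustment restores power to near 90% whatever the gap. It does not. The 10 points in section 14.1 are a crude difference in change. Treating them as the effect given baseline and adding a 6-point gap implies a crude difference of 10 + 6 × (1 − slope), that is 12.4 to 13.6. With the crude difference held at 10, adjusted power is only about 45-62%.

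Other objections carry less weight. Section 14.4 is a summary that defers detail to the SAP, but it already names the test. Section 14.11 allows adjustment, but only as exploratory work, for factors found imbalanced, and directed at the primary analysis. The descriptive wording in section 2.3.2 conflicts with 14.4 and 14.8 and does not override them. It is true that the primary conclusion does not rest on these tests.

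**Conclusion.** The point holds for the two absolute-threshold endpoints. As written, their repeat of the primary comparison tests a different hypothesis from the primary ANCOVA, and any baseline difference between the biomarker groups enters the result. The effect ranges from none with equal baselines to a false-rejection rate of 13-23% at an 8-point CDAI gap, under assumed means, SDs and slopes. The protocol does not say where in that range the trial lies. A reader might extend the criticism to every binary endpoint, but ACR50 is defined relative to each patient's baseline (section 7.6.11) and is little affected. HAQ-DI and SF-36 are continuous and fall outside the χ² sentence. The primary analysis and the sample size are untouched. This is an inexpensive improvement, held with moderate confidence.

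**What to change.** In sections 14.4 and 14.8, for Group 1 against Group 3:

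- Analyse the DAS28 threshold and CDAI remission by logistic regression on biomarker status plus the continuous baseline value of the same index. Use Firth penalisation if events are sparse.
- Report a standardised risk difference with a 95% confidence interval. Keep crude proportions and the χ²/Fisher result as unadjusted description or sensitivity.
- Treat adjustment of ACR50 as optional, for consistency.
- Reconcile the descriptive-only statement in section 2.3.2 with 14.4 and 14.8, and the DAS28 cut-off between 2.3.2 and 2.5.
- State that adjustment removes measured baseline severity only and that the comparison remains non-randomised.

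The cost is wording and a slightly more complex model. Baseline CDAI and DAS28 are already collected (sections 7.2 and 7.5.3), and no patients are added.

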#### 14.9 Safety analysis

The safety analysis set consists of patients who received at least one dose of the trial medication. Safety analysis will be based on the safety analysis set. All AEs will be recorded, notified, assessed for seriousness, and severity, reported, analysed and managed in accordance with the Medicines for Human Use (Clinical Trials) Regulations 2004. The reporting and notification of serious adverse events (SAEs) and suspected unexpected serious adverse reactions (SUSARs) is specified in the protocol and these events will be summarised by treatment and pathotype.

#### 14.10 Subgroup analyses

Response in individual treatment groups, both overall and by arm, will be presented descriptively.

#### 14.11 Adjusted analysis

Baseline factors will be tested for imbalance between groups. As part of additional exploratory analyses, any imbalanced baseline factors will be considered as covariates in statistical models to determine the effect, if any, of adjusting models with these factors, if this is deemed clinically or biologically appropriate, to determine the robustness of the primary analysis.

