#### 14.5 Summary of baseline data and flow of participants

Baseline characteristics and clinical data for randomised patients will be summarised but not subjected to statistical testing. All participating sites will be asked to keep a log of consented patients who were screen failures. Reasons for non-participation will be categorised and summarised. Participation in the trial, treatment allocation and completeness of follow-up will be illustrated by a CONSORT flow diagram.

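### Section 14.11 tests baseline factors for imbalance, which Section 14.5 rules out, and this weak screen selects the only adjustment beyond baseline CDAI described for Group 1 vs Group 3

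*Protocol*

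**What the plan says.** Section 14.5 of the protocol: "Baseline characteristics and clinical data for randomised patients will be summarised but not subjected to statistical testing". Section 14.11: "Baseline factors will be tested for imbalance between groups". Section 14.11 then says what the tests are for: "any imbalanced baseline factors will be considered as covariates in statistical models". Two qualifiers apply. The models are run "As part of additional exploratory analyses", and a flagged factor is used only "if this is deemed clinically or biologically appropriate, to determine the robustness of the primary analysis". Section 14.11 does not say which groups are compared.

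Section 14.7 defines the primary comparison: "The primary analysis is within the abatacept arm", Group 1 (biomarker positive) against Group 3 (biomarker negative), by "analysis of covariance (ANCOVA) with treatment as a factor and baseline value as continuous covariate". Sections 2.2 and 14.8 add a secondary contrast, (Group 1 minus Group 2) against (Group 3 minus Group 4), which uses the placebo patients in each biomarker stratum. Section 7.3 randomises drug against placebo within biomarker strata.

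**The concern.** All patients in Groups 1 to 4 are randomised patients, so Section 14.5 covers them all. Any SAP written under this protocol must breach either 14.5 or 14.11.

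The selection rule is also poor under either meaning of groups. Between drug and placebo, allocation is random, so a significant baseline difference is a chance finding. Between Groups 1 and 3, biomarker status is a patient characteristic and imbalance is to be expected. A non-significant test in a modest sample is then no evidence that a factor can be ignored.

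Section 14.1 intends to attribute the Group 1 vs Group 3 difference to the biomarker profile. A check that adjusts only for factors that happen to reach significance, and only if they are then judged suitable, gives that attribution little support.

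**Working it through.** **The plan's own figure.** Inputs from Section 14.1: difference 10, SD 14.34, power 90% or 80%. Two-sided alpha of 0.05 is assumed, because 14.1 does not state it.

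n per group = 2 × (1.960 + 1.282)² × 14.34² / 10² = 43.2, so 44 per group, 88 for the comparison and 176 for four groups. At 80% power, 2 × (1.960 + 0.842)² × 14.34² / 10² = 32.3, so 33 per group, 66 and 132. Allowing 10% attrition: 176/0.90 = 195.6, so 196, and 132/0.90 = 146.7, so 147. All figures agree with the protocol, so 44 per group is the right size for the next steps.

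**How often the imbalance test works.** Two-sample t test, 44 per group, 5% level. The critical t on 86 degrees of freedom is 1.988, so an observed imbalance must exceed 1.988 × √(2/44) = 0.424 SD to be flagged.

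**Bias left when the test misses.** Omitting a factor biases the group difference by (imbalance in the sample, in SD) × (correlation with change in CDAI) × 14.34. In trials where the test misses, the sample imbalance is by construction below 0.424 SD, so its mean is smaller than the true imbalance. With s = √(2/44) = 0.213 and a true imbalance of 0.4, the truncated-normal mean is 0.4 − 0.213 × (0.396 − 0.000)/0.544 = 0.245 SD. The bias at correlation 0.3 is 0.245 × 0.3 × 14.34 = 1.1 points. A simulation of 200,000 trials per row gives the same:

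| True imbalance (SD) | Detected | Missed | Mean imbalance when missed (SD) | Bias, correlation 0.3 | Bias, correlation 0.5 |
|---|---|---|---|---|---|
| 0.2 | 15.3% | 84.7% | 0.144 | 0.6 | 1.0 |
| 0.3 | 28.5% | 71.5% | 0.200 | 0.9 | 1.4 |
| 0.4 | 45.8% | 54.2% | 0.245 | 1.1 | 1.8 |
| 0.5 | 64.0% | 36.0% | 0.281 | 1.2 | 2.0 |

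The imbalances and correlations are assumptions; the protocol gives neither. The correlation should be read as what remains after baseline CDAI, which is already in the primary model.

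**The opposite error.** If 10 independent factors were truly balanced, as between randomised arms, at least one would be flagged with probability 1 − 0.95¹⁰ = 40%. Correlated factors would lower this.

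**Effect of the selection step on false positives.** Simulation, 44 per group, one confounder, imbalance 0.3 or 0.5 SD, correlation 0.3 or 0.5, no other covariate, 20,000 trials per setting:

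| Analysis | False-positive rate |
|---|---|
| Unadjusted | 7.0% to 20.8% |
| Adjusted only if the test is significant | 5.2% to 5.7% |
| Prespecified covariate | 4.8% to 5.1% |

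**The case against.** A reader might infer that 14.11 is the only control of confounding in the trial. It is not. The primary ANCOVA carries baseline CDAI, and the secondary contrast has randomised placebo controls in each stratum. Nor does 14.11 touch the primary estimate or its p-value, since its models are expressly exploratory.

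A reader might also take the missing covariate list as the fault. Section 14.4 leaves detail to the SAP, which is not shown, so that omission is not a finding. What can be criticised is the rule that the protocol itself fixes.

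The full 0.4 SD imbalance would give 0.4 × 0.3 × 14.34 = 1.7 points, but that overstates the bias in the trials where the test misses; 1.1 is the matching figure.

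An automatic test-then-adjust rule with one confounder does little harm to the false-positive rate, as the last table shows. This stands. It applies less well to 14.11 as written, where flagged factors are only considered and may be set aside on judgement.

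The evidence for confounding is indirect. Section 1.1 reports, for histological pathotype, that "The lympho-myeloid phenotype was found to be associated with the highest level of erythrocyte sedimentation rate (ESR") among other markers. The trial biomarker is CD80/CD86, and no section gives its association with those markers. Section 2.1 does word the hypothesis in terms of the lymphoid pathotype, so the link is plausible but not shown.

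Finally, CRP, ESR and anti-CCP may express the same synovial biology as the biomarker, so adjusting for them could remove part of the effect of interest. This also stands and shapes the fix.

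**Conclusion.** The point holds in limited form. Sections 14.5 and 14.11 contradict each other on testing baseline data; this rests on the text alone. Beyond baseline CDAI, the test-based rule in 14.11 is the only covariate adjustment described for a primary comparison that randomisation does not balance, and it is a poor screen: at 44 per group it misses a 0.3 SD imbalance 71.5% of the time and a 0.4 SD imbalance 54% of the time. Under the assumed imbalances and correlations, a missed factor leaves about 0.6 to 2.0 CDAI points, or 6% to 20% of the planning difference of 10.

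The consequence is a robustness check that is weak and open to selection after the data are seen. The documents do not support the stronger conclusion that the primary result is biased by 14.11, or that CD80/CD86 status is known to be confounded. The change should be made, but the fault is a moderate one.

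**What to change.** Delete the imbalance tests from Section 14.11 and leave Section 14.5 as written. In their place, prespecify one adjusted sensitivity analysis of Group 1 vs Group 3, fixed before unblinding and before outcomes are examined by group, and reported beside the primary result whatever the baseline tables show. It should add to baseline CDAI a short list of prognostic factors recorded before treatment, for example age, sex, symptom duration, RF/anti-CCP status, CRP or ESR, and baseline steroid use.

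The cost is a wording change and no new data. Six added terms, one parameter each, reduce the residual degrees of freedom from 88 − 3 = 85 to 79. The sample size stays the same. Because markers such as CRP, ESR and anti-CCP may lie close to the biomarker's own biology, present the result as a sensitivity analysis and leave the primary model unchanged. The adjustment does not replace the placebo-controlled secondary contrast as evidence that the biomarker predicts response to abatacept in particular.

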## 14.12 Interim analysis and criteria for the premature termination of the study

There are no planned interim analyses, unless specifically requested by the Trial Steering Committee and these would be reported in a confidential closed session.

#### 14.13 Procedure(s) to account for missing or spurious data

Data cleaning will be performed as documented in the trial Data Management Plan. The Early RA 3TR Database has in-built data checks and validations to ensure a complete and accurate dataset, supplied by Webclinica. These data checks and validations will generate an autoquery if a field is left blank (in most cases the user will be unable to save the page unless the field is completed or indicated as not done) or a value is outside the expect range. The trial coordinating office can generate manual queries as needed within the database. A database user manual will be provided to sites.

Where an assessment has not been done or a particular value within an assessment is not available for any reason, there is an option for the site to record "not done". Sites will be prompted to provide the reason via an automatic query generated by the database. If any data is changed after the initial completion of the eCRF, sites will be prompted to record the reason why.

Missing data for essential outcome variables and their subcomponents will be handled by multiple imputation by chained equation (MICE), incorporating longitudinal datapoints. Imputation will be performed five times and the mean (or median, if a particular variable is not Gaussian) result of imputation will be used to replace missing values. Imputed values will be checked for excessive variability across the five imputation runs.

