## 14.0 Statistical and data analysis

#### 14.1 Sample size calculation

The primary analysis of the trial is the comparison between Group 1 and Group 3 (see figure in Section 2.6), i.e. the patients classified as biomarker positive treated with Abatacept + Methotrexate (MTX) (Group 1) vs. the patients classified as biomarker negative treated with Abatacept + Methotrexate (MTX) (Group 3). Since patients will be randomised 1:1 to either Abatacept + MTX or Placebo + MTX and the median value observed in the PEAC study as a cut-off to classify the biomarker status, we expect the comparison groups to be roughly equal. That would allow to ascribe the differences in response we will observe to the different biomarker profiles of the two groups, hence demonstrating if the presence of a biomarker will enhance the response to the any of the drugs included in the trial.

The power calculation is done for this comparison, based on the following assumptions:

50% patients will be classified as biomarker positive and 50% as biomarker negative
 Using change in CDAI score from baseline (delta CDAI) as the primary outcome, a difference in delta CDAI between the two comparison groups of 10, with a Standard Deviation of 14.34. These are the values that were observed when analysing the difference in delta CDAI between biomarker positive and biomarker negative patients treated with MTX in the PEAC study. Although PEAC patients were not treated with Abatacept, this comparison is expected to be even more in favour of the biomarker positive group using Abatacept together with MTX. Thus, basing the power calculation on the PEAC observed difference is a conservative assumption.

With these assumptions, 88 patients would be needed to detect a significant difference of 10 in delta CDAI with 90% power (66 patients for 80% power). Since this would only be for Group 1 and Group 3 (44 patients each), a total of 176 patients would be sufficient for 90% power in the whole trial (132 for 80% power) which includes all four groups as per Figure 1 Section 2.6. If we assume a 5% dropout rate and also account for an expected 5% of patients that have insufficient RNA for the Nano-string analysis (based on results from the STRAP trial), 196 patients in the whole trial would be sufficient to detect a significant difference (Group 1 vs Group 3) of 10 in delta CDAI with 90% power (147 patients for 80% power).

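### Section 14.13 collapses five imputations into one filled-in data set, so the primary standard error is too small: modestly at the planned 5% dropout, materially at 10% to 20% missing

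*Protocol*

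**What the plan says.** Protocol Section 14.13 covers essential outcome variables and their subcomponents. Missing values "will be handled by multiple imputation by chained equation (MICE), incorporating longitudinal datapoints". The combination rule follows: "Imputation will be performed five times and the mean (or median, if a particular variable is not Gaussian) result of imputation will be used", and this "result of imputation will be used to replace missing values". The only use made of the spread between runs is a check: "Imputed values will be checked for excessive variability across the five imputation runs".

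The analysis sections describe one model fitted once. Section 14.7: "The primary outcome will be analysed by analysis of covariance (ANCOVA) with treatment as a factor and baseline value as continuous covariate". It continues: "The treatment effect will be reported as least squares mean with 95% confidence intervals". Section 14.4 gives a single chi-squared or Fisher test for each binary secondary endpoint. No section mentions analysing each imputed data set or pooling results.

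**The concern.** Multiple imputation gives valid standard errors because the analysis is repeated in each completed data set and the variance between the results is added to the variance within them. Section 14.13 averages the imputed values instead of the estimates. The result is single imputation close to the conditional mean, with two consequences.

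- **Primary analysis.** Averaged values carry little residual noise, yet the ANCOVA counts each as a full observation. The residual variance is understated and the sample size overstated, so the interval is too narrow and the test rejects too often.
- **Responder endpoints.** ACR50, the DAS28 threshold and CDAI remission are cut-offs applied to components. Averaging before applying a cut-off pulls values towards the centre, so too few imputed patients fall in the tail when the true rate is low.

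The protocol does not leave this step open; it fixes a rule. An analysis plan that used Rubin's rules would have to contradict Section 14.13.

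**Working it through.** **1. The plan's own figure.** Section 14.1 assumes "a difference in delta CDAI between the two comparison groups of 10, with a Standard Deviation of 14.34" and concludes that "88 patients would be needed to detect a significant difference of 10 in delta CDAI with 90% power". Alpha is not stated there; 0.05 two-sided is assumed, in line with the 95% interval. The standard two-sample formula gives 2 × (1.960 + 1.282)² × 14.34² / 10² = 43.2 per group, or 44 with the t correction. That is 88 in all, and 33 per group at 80% power. Then 176 / 0.90 = 195.6, so 196, and 132 / 0.90 = 146.7, so 147. All the stated figures reproduce.

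**2. Hand check of the primary SE.** Take the least favourable case: no post-baseline value is available and outcomes are missing completely at random in a share p.

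- Averaging five draws leaves about one fifth of the residual variance in each imputed value. The residual variance seen by the ANCOVA is therefore multiplied by (1 - p) + p/5 = 1 - 0.8p.
- The true variance of the estimate, relative to complete data, is about (1 + p/5) / (1 - p).
- Reported SE / true SE ≈ √[(1 - 0.8p)(1 - p) / (1 + p/5)].
- Type I error ≈ 2 × [1 - Φ(1.96 × ratio)].

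Results:

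- p = 0.05: √(0.96 × 0.95 / 1.01) = 0.950; error 6.3%
- p = 0.10: √(0.92 × 0.90 / 1.02) = 0.901; error 7.7%
- p = 0.20: √(0.84 × 0.80 / 1.04) = 0.804; error 11.5%

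**3. Simulation.** 4,000 trials per setting, 88 patients, SD 14.34, no true difference, missing completely at random, five proper normal imputations. Assumed, because the protocol gives no values: correlation of baseline with change -0.4, and of week 12 with week 16 0.7. The averaged-value ANCOVA is compared with Rubin's rules (Barnard-Rubin degrees of freedom) on the same imputations. Each cell shows without / with a week 12 value.

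| Missing | Reported SE / true SD | Type I error, averaged | Type I error, Rubin |
|---|---|---|---|
| 5% | 0.952 / 0.966 | 6.2% / 5.8% | 4.8% / 4.9% |
| 10% | 0.897 / 0.939 | 8.0% / 6.2% | 4.8% / 4.6% |
| 20% | 0.798 / 0.872 | 11.4% / 8.8% | 4.9% / 4.7% |

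Simulation error near 5% is √(0.05 × 0.95 / 4000) = 0.34 percentage points. At 5% missing without week 12, the mean SE from Rubin's rules is 2.90 against a true SD of 2.89; the averaged analysis reports 2.75. The mean estimate of the difference was not biased.

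Runs under other assumed correlations and dropout times widen the ranges slightly:

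- 5% missing: SE about 1-5% too small, error about 5-6%
- 10% missing: about 5-10% and 6-8%
- 20% missing: about 13-21% and 8-12%

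The lower ends apply when a late visit such as week 12 is available for imputation.

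**4. Responder rates.** Let the imputation model explain a share R² of the outcome variance. The mean of five draws then has relative variance v = R² + (1 - R²)/5, and a true rate π becomes Φ(Φ⁻¹(π)/√v) among imputed patients.

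- π = 25%, R² = 0.2: v = 0.36, Φ(-0.674/0.60) = 13.0%
- π = 25%, R² = 0.7: v = 0.76, Φ(-0.674/0.872) = 22.0%
- π = 15%, over the same R² range: 4.2% to 11.7%
- π = 50%: unchanged

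For the whole group with π = 25% and 5% missing: 0.95 × 25% + 0.05 × 13.0% = 24.4% at worst, 24.9% at best. At 20% missing: 22.6% to 24.4%.

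**The case against.** **Little may be missing.** The only dropout figure in the protocol is 5% (Section 14.1). The further 5% with insufficient RNA are withdrawn before randomisation (Sections 7.3 and 8.1) and create no missing week 16 outcome. Section 8.2 asks patients who stop treatment to attend week 16. CDAI is scheduled every four weeks and Section 14.13 uses the longitudinal values, which favours the lower ends of the ranges. All of this stands, and it limits the size of the error. It does not remove it: 5% is a planning assumption about dropout, single components may be recorded as not done, and consent to further visits can be withdrawn.

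**The text might be loose wording for ordinary pooling.** It is true that the protocol never says in terms that filled-in values are analysed as if observed; that is an inference. But the text says the averaged result replaces the missing values, and Sections 14.4 and 14.7 describe single analyses.

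**Stronger readings the documents do not support.**

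- A reader might infer that the primary test has a type I error near 10%. That needs about 20% missing, four times the planned dropout.
- A reader might infer that every responder endpoint is biased. Rates near 50% are not shifted, and Section 2.3.2 calls the secondary endpoints descriptive within groups, although Sections 14.4 and 14.8 also test or compare them.
- A reader might illustrate the problem with one patient: predicted CDAI 12, SD 8, chance of remission (2.8 or less) 12.5%, falling to 0.5% for a mean of five draws. Those inputs are in no document. The normal curve also puts Φ(-1.5) = 6.7% below zero, which CDAI cannot reach. Truncated at zero, the chance is (12.5 - 6.7) / 93.3, about 6%.
- A reader might take the check on variability between runs as a second fault. No action is attached to it, and it is an ordinary diagnostic.

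**Conclusion.** The point holds. Section 14.13 as written turns multiple imputation into single imputation, and the error favours false positives in the confirmatory comparison. At the planned 5% the effect is modest, and some of the simulated error rates there lie close to nominal. At 10% it is noticeable and at 20% it is serious. The distortion of responder rates matters mainly for low-rate endpoints such as remission and for higher missingness.

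The sizes rest on normal outcomes, data missing completely at random, averaging by the mean and assumed correlations. The direction of the SE error does not depend on the correlations chosen. The sample size in Section 14.1 is unaffected.

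**What to change.** Replace the averaging sentence in Section 14.13 with wording such as:

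*The imputed data sets will be kept separate; CDAI, DAS28, ACR50 and remission status will be derived within each; the analysis model will be fitted in each; and estimates and variances will be combined by Rubin's rules.*

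The check on variability across runs may stay as a diagnostic. The number of imputations and the imputation model can be set in the SAP. More than five imputations is advisable, although five already gave close to nominal error under Rubin's rules.

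The cost is a short wording change, minor programming, and slightly wider, correct intervals. It should be made before the data are analysed, since a later change to the missing-data rule could look driven by the results.
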